8.4.8. Infections

Investigators are required to evaluate participants for any signs or symptoms of infection at scheduled visits. Study intervention administration should not be given to a participant with a clinically significant, active infection. If a participant develops a serious infection, discontinuation of study intervention should be considered.

8.4.9. Tuberculosis Evaluations

8.4.9.1. Initial Tuberculosis Evaluation

Participant medical history assessment must include specific questions about a history of TB or known occupational or other personal exposure to individuals with active TB. The participant should be asked about past testing for TB, including chest imaging results and responses to tuberculin skin or other TB testing. Investigators have the option to use the tuberculin skin test in addition to IGRA testing to screen for latent TB if preferred by local health authorities, or if they believe based on their judgment that both tests are clinically indicated to evaluate a participant at high risk for latent TB.

Participants with a negative IGRA test result are eligible to continue with pre-randomization procedures. Participants with a newly identified positive IGRA test result must undergo an evaluation for active or latent TB, or suspected false-positive initial testing, and initiate appropriate treatment if needed. Appropriate treatment for latent TB is defined according to local country guidelines for immunocompromised patients. If no local country guidelines for immunocompromised patients exist, US guidelines must be followed.

Participants with indeterminate/borderline IGRA test results should have the test repeated. Participants with persistently indeterminate/borderline IGRA test results may be randomized or continued in the trial without treatment for latent TB, if active TB is ruled out, chest imaging shows no abnormality suggestive of TB (active or inactive), and the participant has no additional risk factors for TB as determined by the investigator. This determination must be promptly reported to the sponsor's medical monitor and recorded in the participant's source documents and initialed by the investigator.

8.4.9.2. Ongoing Tuberculosis Evaluation

To aid in the early detection of TB infection or exposure during study participation, participants must be evaluated for TB signs, symptoms, and close contacts at scheduled visits (refer to Section 1.3) or by telephone approximately every 8 to 12 weeks. The following series of questions is suggested for use during the evaluation:

- "Have you had a new cough of > 14 days' duration or a change in a chronic cough?"
- "Have you had any of the following symptoms:

Persistent fever?

Unintentional weight loss?

Night sweats?"

"Have you had close contact with an individual with active TB?" (If there is uncertainty as
to whether a contact should be considered "close," a physician specializing in TB should be
consulted.)

If the evaluation raises suspicion for TB infection or the participant has had a close contact exposure to TB, study intervention must be withheld and an immediate and thorough investigation must be undertaken, including consultation with a physician specializing in TB to determine if treatment is warranted prior to any further study intervention. Participants should be encouraged to return for all subsequent scheduled study visits according to the protocol.

Note: Investigators should be aware that TB reactivation in immunocompromised participants may also present as extrapulmonary or disseminated disease.

8.5. Adverse Events, Serious Adverse Events, and Other Safety Reporting

Timely, accurate, and complete reporting and analysis of safety information, including AEs, SAEs, and PQCs, from clinical studies are crucial for the protection of participants, investigators, and the sponsor, and are mandated by regulatory agencies worldwide. The sponsor has established Standard Operating Procedures in conformity with regulatory requirements worldwide to ensure appropriate reporting of safety information; all clinical studies conducted by the sponsor or its affiliates will be conducted in accordance with those procedures.

Adverse events will be reported by the participant (or, when appropriate, by a caregiver, surrogate, or the participant's legally acceptable representative) for the duration of the study.

For study intervention that meets the definition of a combination product, malfunctions or deficiencies of a device constituent will be reported as a PQC.

Further details on AEs, SAEs, and PQCs can be found in Appendix 4: Adverse Events, Serious Adverse Events, Product Quality Complaints, and Other Safety Reporting: Definitions and Procedures for Recording, Evaluating, Follow-up, and Reporting.

8.5.1. Time Period and Frequency for Collecting Adverse Event and Serious Adverse Event Information

All Adverse Events

All AEs and special reporting situations, whether serious or non-serious, will be reported from the time a signed and dated ICF is obtained until completion of the participant's last study-related procedure, which may include contact for follow-up of safety.

Serious Adverse Events

All SAEs occurring during the study must be reported to the appropriate sponsor contact person by study site personnel immediately, but no later than 24 hours of their knowledge of the event.

Serious adverse events, including those spontaneously reported to the investigator within 12 weeks after the last dose of study intervention, must be reported. The sponsor will evaluate any safety information that is spontaneously reported by an investigator beyond the time frame specified in the protocol.

A **possible Hy's law Case** is defined by the occurrence of ALT/AST ≥ 3 x ULN, alkaline phosphatase (ALP) < 2 x ULN together with total bilirubin ≥ 2 x ULN or International Normalized Ratio (INR) > 1.5 (if measured) (see Appendix 10.7). Any possible Hy's Law case is considered an important medical event and must be reported to the sponsor in an expedited manner, even before all other possible causes of liver injury have been excluded. A confirmed Hy's law case must be reported as a SAE.

Information regarding SAEs will be transmitted to the sponsor using the Serious Adverse Event Form, which must be completed and signed by a physician from the study site, and transmitted to the sponsor immediately but no later than within 24 hours. The initial and follow-up reports of an SAE should be made by facsimile (fax). Telephone reporting should be the exception and the reporter should be asked to complete the appropriate form(s) first.

8.5.2. Method of Detecting Adverse Events and Serious Adverse Events

Care will be taken not to introduce bias when detecting AEs or SAEs. Open-ended and nonleading verbal questioning of the participant is the preferred method to inquire about AE occurrence.

Solicited Adverse Events

Solicited AEs are predefined as site reactions and systemic events for which the participant is specifically questioned.

Unsolicited Adverse Events

Unsolicited AEs are all AEs for which the participant is not specifically questioned.

8.5.3. Follow-up of Adverse Events and Serious Adverse Events

The investigator is obligated to perform or arrange for the conduct of supplemental measurements and evaluations as medically indicated to elucidate the nature and causality of the AE or SAE as fully as possible. This may include additional laboratory tests or investigations, histopathological examinations, or consultation with other health care professionals.

Adverse events and the special reporting situation of pregnancy, will be followed by the investigator as specified in Appendix 4: Adverse Events, Serious Adverse Events, Product Quality Complaints, and Other Safety Reporting: Definitions and Procedures for Recording, Evaluating, Follow-up, and Reporting.

8.5.4. Regulatory Reporting Requirements for Serious Adverse Events and Anticipated Events

The sponsor assumes responsibility for appropriate reporting of AEs to the regulatory authorities. The sponsor will also report to the investigator (and the head of the investigational institute where required) all suspected unexpected serious adverse reactions (SUSARs). The investigator (or sponsor where required) must report SUSARs to the appropriate Independent Ethics Committee/Institutional Review Board (IEC/IRB) that approved the protocol unless otherwise required and documented by the IEC/IRB. A SUSAR will be reported to regulatory authorities unblinded. Participating investigators and IEC/IRB will receive a blinded SUSAR summary, unless otherwise specified.

An anticipated event is an AE that commonly occurs in the study population independent of exposure to the drug under investigation. For the purposes of this study the following SAEs will be considered anticipated events:

- Adverse events related to symptoms of Crohn's disease
- Adverse events related to worsening or progression of Crohn's disease

These anticipated events will be periodically analyzed in aggregate by the sponsor during study conduct. The sponsor will prepare a safety report in narrative format if the aggregate analysis indicates that the anticipated event occurs more frequently in the intervention group than in the control group and the sponsor concludes there is a reasonable possibility that the drug under investigation caused the anticipated event.

The plan for monitoring and analyzing the anticipated events is specified in a separate Anticipated Events Safety Monitoring Plan. The assessment of causality will be made by the sponsor's unblinded safety assessment committee.

The sponsor assumes responsibility for appropriate reporting of the listed anticipated events according to the requirements of the countries/territories in which the studies are conducted.

8.5.5. Pregnancy

All initial reports of pregnancy in female participants or partners of male participants must be reported to the sponsor by the study site personnel within 24 hours of their knowledge of the event using the appropriate pregnancy notification form. Abnormal pregnancy outcomes (eg, spontaneous abortion, fetal death, stillbirth, congenital anomalies, ectopic pregnancy) are considered SAEs and must be reported using an SAE reporting form. Any participant who becomes pregnant during the study must be promptly withdrawn from the study and discontinue further study intervention.

Follow-up information regarding the outcome of the pregnancy for female participants who become pregnant, or where the pregnancy was the result of male participant and his partner, and any postnatal sequelae in the infant will be requested.

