- b: If clinically appropriate and allowed by local regulations, the Week 156 visit can be done by telephone and no labs drawn.
- c: If a flare visit coincides with a scheduled visit, procedures for the scheduled visit should be performed, along with any additional procedures required by a flare visit. Flare visit blood tests are not required if performed within 2 weeks of the Flare visit.
- d: Early termination visits should ideally take place approximately 12 weeks after last study intervention administration, though if a patient intends to withdraw their consent sooner than this milestone the ET visit should be scheduled as needed to accommodate with the patient's intent.
- e: Blood collected from one venipuncture will be divided into multiple aliquots of serum for the measurement of guselkumab concentration, antibodies to guselkumab, and a back-up sample. Details will be provided in the Laboratory Manual.
- f: Ileocolonoscopy does not need to be repeated if an ileocolonoscopy for a flare visit occurred within 12 weeks of the visit date, unless patient and investigator wish to, for example due to subsequent change in clinical status.

Key: AE = adverse event; CD = Crohn's disease; CDAI = Clinical Disease Activity Index; CRP = C-reactive protein; CT = computed tomography; C-SSRS = Columbia Suicide Severity Rating Scale; eCRF = electronic case report form; ET = Early Termination; HBV = hepatitis B virus; HCV = hepatitis C virus; HIV = human immunodeficiency virus; IGRA = interferon gamma release assay; OTC = over the counter; PK = pharmacokinetics; PRO = patient-reported outcome; PROMIS = Patient-Reported Outcomes Measurement Information System; CCI ; TB = tuberculosis; WPAI = Work Productivity Impairment.

Cross Over (CO) Schedule of Activities (Follow if participant meets cross over criteria)

		`		•	Study Visits				
Study Procedure	COp	CO+8 wks	CO+16 wks ^c	Every 16 wks (up to Week 128)	Week 144 - Final Dosing Visit ^e	Week 152 - Final Efficacy Visit ^f	Week 156 -Final Safety Visit ^g	Early Terminati on Visit	Notes
Directed physical exam, with full physical exam where noted (F)	X	X	X	X	X	X(F)		X	Directed physical exam for abdominal mass and fistulas at all visits.
Urine pregnancy test	X	X	X	X	X	X			Must be performed at on-site visits prior to dispensing study intervention in participants of childbearing potential.

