CDAI assessment	X	X	X	Х	X	X		X	For calculation of CDAI. CDAI: The hematocrit value obtained during screening will be used to calculate CDAI at Week 0. For all other visits, the most recent hematocrit value obtained will be used to calculate the CDAI.
Weight (component of CDAI)	X	X	X	X	X	X		X	In kilograms (kg)
Fistula assessment	X	X	X	X	X	X		X	

					Study Visits	Week) ^a			
Study Procedure	COp	CO+8 wks	CO+16 wks ^c	Every 16 wks (up to Week 128)	Week 144 - Final Dosing Visit ^c	Week 152 - Final Efficacy Visit ^f	Week 156 -Final Safety Visit ^g	Early Terminati on Visit	Notes
Video ileocolonoscopy with biopsy and histology			X			X			XO+16 [OPTIONAL] May be performed between week 16 and 24. If performed on the day of the designated visit, the 7 days before the initiation of the colonoscopy preparation should be utilized to calculate CDAI scores for these visits. Final efficacy visit ileocolonoscopy does
									not need to be repeated if the XO+16 ileocolonoscopy occurred within 24 weeks of the visit date
Stool sample (fecal calprotectin)	X		X			X			
WPAI-CD	X		X			X		X	
PROMIS-29	X		X			X		X	
PROMIS Fatigue 7a	X		X			X		X	
Crohn's disease-related hospitalizations and surgeries	X	X	X	X	X	X	X	X	Items to be recorded are listed in the healthcare resource utilization worksheet.
Administer (or dispense) study intervention ⁱ	х	X	Х	X	X				All assessments described in this table are to be completed prior to study intervention administration, unless otherwise specified. PRO assessments should be completed first, and then any other clinical procedures, tests, or consultations. Cross over dosing: GUS 400 mg SC at CO, CO+4 (home dose), CO+8; and then CCI every 8 weeks (every other maintenance dose after the CO+16 visit will be home administration.
Record drug accountability	X	X	X	X	X			X	Participants will return study intervention packaging (cartons) when administered at home, for drug accountability, including any unadministered syringes.

CONFIDENTIAL – FOIA Exemptions Apply in U.S.

Footnotes:

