Participants who discontinue study intervention early will return for an early termination visit at least 12 weeks after study intervention discontinuation, which will also serve as their final safety visit. This visit will include a video ileocolonoscopy at the time of discontinuation, except those participants who have already had demonstrated endoscopic recurrence in a study ileocolonoscopy.

Study Length

After the screening period, the total study duration is 156 weeks, with the final dose of study intervention given at Week 144 and the final efficacy visit at Week 152 followed by the final safety visit at Week 156. The end of the study is defined as when all participants have completed the Week 156 visit assessments, or have terminated study participation prior to Week 156 and had their last follow-up assessment (12 weeks after the last dose of study intervention or at early termination visit).

The main study period is defined as when the last randomized participant has completed the Week 48 assessments at which point the main study database lock will occur. Participant follow-up for the main study period may vary depending upon when they enrolled in the trial (estimated to be from 12 to 30 months, based upon an anticipated accrual time of 18 months, but with an upper limit of 36 months [total study treatment duration], should accrual time exceed 18 months).

Endpoints

The primary endpoint is endoscopic recurrence prior to or at Week 48. Video ileocolonoscopy will be performed at the Week 48 visit and centrally read, using a definition of a modified Rutgeerts score of \geq i2a disease activity to define endoscopic recurrence.

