7. DISCONTINUATION OF STUDY INTERVENTION AND PARTICIPANT DISCONTINUATION/WITHDRAWAL

7.1. Discontinuation of Study Intervention

A participant's study treatment should be discontinued if:

• The investigator or the medical monitor believes that for safety reasons (eg, an AE) it is in the best interest of the participant to stop treatment.

- The participant becomes pregnant or plans a pregnancy within the study period or within 12 weeks after the last study intervention administration.
- The participant meets **ANY** of the following TB related conditions:
 - A diagnosis of active TB is made.
 - A participant has symptoms suggestive of active TB based on follow-up assessment questions and/or physical examination or has had recent close contact with a person with active TB and cannot or will not continue to undergo additional evaluation.
 - A participant undergoing evaluation has chest imaging with evidence of current active TB and/or a positive IGRA test result, unless active TB can be ruled out and appropriate treatment for latent TB can be initiated prior to the next administration of study intervention and continued to completion.
 - A participant receiving treatment for latent TB discontinues this treatment prematurely or is noncompliant with the therapy.
- The participant has a serious adverse reaction that is related to an bronchospasm with wheezing and/or dyspnea that requires ventilatory support OR that results in symptomatic hypotension with a decrease in systolic blood pressure >40 mm Hg or blood pressure <90/60 mm Hg. In general, discontinuation of study intervention administration must be considered for participants who develop non-serious, but severe
- The participant develops a malignancy including squamous cell skin cancer. Consideration may be given to allow participants to continue to receive study intervention if they develop ≤2 basal cell skin cancers that are adequately treated with no evidence of residual disease.
- The initiation of the following protocol-prohibited medications at any time during the study as listed in Section 6.8.2.
- A serious opportunistic infection occurs.
- The participant (or the participant's representative) withdraws consent (or assent) for further administration of study intervention.

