- The participant has CD-related surgeries that will preclude the future ability to assess efficacy through the CDAI. Surgeries that are thought to represent a lack of efficacy of study intervention should be considered for discontinuation at the discretion of the Investigator other than minor procedures (eg, placement of a seton or cutaneous drainage of an abscess).
- The participant has severe liver test abnormalities that are not transient and are not explained by other etiologies; see Section 10.7 for definitions of abnormal values.
- The participant reports suicidal ideation with intention to act ("Ideation level 4"), suicidal ideation with specific plan and intent ("Ideation level 5"), or any suicidal behavior (interrupted suicide attempt, aborted suicide attempt, or preparatory behaviors for making a suicide attempt) on a post-baseline C-SSRS assessment. If a participant can be adequately treated with psychotherapy and/or pharmacotherapy based on an evaluation by a mental health professional, then the participant, at the discretion of the investigator, may be continued with treatment if agreed to by the medical monitor or designee. Discussion of such participants with the medical monitor or designee is required.

• A participant who has crossed over to receive open-label treatment with guselkumab and is assessed not to have subsequently attained improvement, in the investigator's judgement (recommended to be initially assessed approximately 16-24 weeks after initiating open-label guselkumab treatment).

Participants who discontinue study intervention (for the reasons above) before the end of planned study treatment (Week 144), should not terminate their study participation (unless enrolling in an investigational advanced therapy CD study or initiating commercial guselkumab prior to cross over to open-label treatment, as described further below). Instead, participants discontinuing study intervention are encouraged to complete study visits through the next 12 weeks, at which time an early termination visit (see SoA, Section 1.3) must be performed. Should the early termination visit be due within 4 weeks of a regularly scheduled visit, it is appropriate to perform the procedures specified for the early termination visit at the appointed time in place of the regular scheduled visit.

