7.2. Participant Discontinuation/Withdrawal From the Study

A participant will be withdrawn from the study for any of the following reasons:

- Lost to follow-up (see Section 7.3)
- Withdrawal of consent for study participation (distinct from desire to/withdrawal of consent to receive further study intervention)
- Death
- Sponsor decision (eg, participating in any other interventional clinical study with an investigational agent or initiating commercial guselkumab treatment prior to cross over to open-label guselkumab treatment)

When a participant withdraws or is withdrawn/terminated prior to study completion, the reason for withdrawal is to be documented in the eCRF and in the source document. These participants should complete the safety and efficacy evaluations specified for the early termination visit in the SoA (Section 1.3). If participants refuse to remain in the study to perform the early termination visit 12 weeks after last study intervention administration, the participant's desire to withdraw their consent for further study participation should be accommodated by performing the early termination visit as soon as necessary/possible. Thus, if possible, the early termination visit should be moved up and performed prior to when the participant might withdraw their consent. If/when a participant decides to withdraw their consent to participate in the study, then no additional assessments are allowed, or can be performed.

Withdrawal of Consent

A participant declining to return for one or more scheduled visits does not necessarily constitute withdrawal of consent. Alternate follow-up mechanisms that the participant agreed to when signing the consent form apply as local regulations permit.

If the participant also chooses to withdraw consent for use of samples for research (refer to Long-Term Retention of Samples for Additional Future Research in Appendix 3: Regulatory, Ethical, and Study Oversight Considerations), samples will be destroyed after they are no longer needed for the clinical study. Details of the sample retention for research are presented in the main ICF.

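### Protocol 8.5.5 withdraws a pregnant participant from the study, while Protocol 7.1 stops only her study intervention and keeps her in follow-up

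*Protocol*

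**What the plan says.** Protocol 8.5.5 (Pregnancy) gives one instruction with two parts: "Any participant who becomes pregnant during the study must be promptly withdrawn from the study and discontinue further study intervention". The same section also asks for follow-up information on the outcome of the pregnancy and on the infant.

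Protocol 7.1 lists reasons for stopping study treatment. One of them is "The participant becomes pregnant or plans a pregnancy within the study period or within" 12 weeks after the last dose. After the list, 7.1 states the consequence: "Participants who discontinue study intervention (for the reasons above) before the end of planned study treatment (Week 144), should not terminate their study participation". It allows two exceptions: joining an investigational advanced therapy study in Crohn's disease, and starting commercial guselkumab before cross over. Everyone else is encouraged to keep attending for 12 more weeks and must then have an early termination visit.

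Protocol 7.2 lists the reasons for withdrawal from the study: loss to follow-up, withdrawal of consent, death and sponsor decision. Pregnancy is not named. Participants who are withdrawn are still asked to complete the early termination evaluations.

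**The concern.** Pregnancy during treatment is foreseeable here. The main Schedule of Activities has urine tests from Week 0 to Week 152 for participants who could become pregnant. When a test is positive, the site needs one rule on whether she stays in the study, and the protocol gives two opposite ones.

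Two things are at stake, both modest:

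- **Safety follow-up.** Section 8.5.1 requires serious adverse events to be reported up to 12 weeks after the last dose, and the early termination visit in 7.1 is timed to close that period. Prompt withdrawal works against it.
- **Outcome data.** Stopping for pregnancy falls under intercurrent event 6 of the primary estimand (discontinuation for other reasons). The strategy is treatment policy, so outcomes observed after the event are used where they exist. Withdrawing the participant makes it less likely that they will.

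**Working it through.** The point concerns consistency of text and the plan has no figure to reproduce. The check is to set the sections side by side for a participant with a positive pregnancy test.

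| Section | Study intervention | Study participation |
|---|---|---|
| 8.5.5 | Stop | Withdraw promptly |
| 7.1 | Stop | Do not terminate; 12 more weeks of visits encouraged, then a mandatory early termination visit |
| 7.2 | Not addressed | Pregnancy not among the named reasons for withdrawal |

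1. **Is the wording of 8.5.5 merely loose?** No. It names leaving the study and stopping study intervention separately, so the first cannot be read as another way of saying the second.
2. **Does 7.1 reach pregnancy?** Yes. Its consequence applies to those who stop for the reasons listed above it, and pregnancy is on that list.
3. **Does an exception in 7.1 let pregnancy out?** No. Both exceptions concern other treatment for Crohn's disease.
4. **Does 7.2 settle it?** No. It does not name pregnancy, and nothing there overrides 7.1.
5. **What does the analysis expect?** Protocol 9.4.2 and SAP Table 7 place discontinuation for other reasons under treatment policy. For time to disease recurrence (SAP Table 10) the equivalent category is number 5, with the same strategy. Both rely on follow-up after study intervention stops, which fits 7.1 and not 8.5.5.
6. **How far does the extra follow-up reach?** Section 7.1 gives 12 weeks. For the Week 48 assessments, 48 − 12 = 36, so a participant who stops at about Week 36 or later could still reach Week 48 under 7.1. One who stops earlier would normally have her early termination visit before Week 48. The gain in observed Week 48 values is therefore confined to late discontinuations.

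**The case against.** The strongest reply is that the conflict has little practical effect. Section 7.2 also sends withdrawn participants to the early termination evaluations. Its default timing is 12 weeks after the last dose, brought forward only if the participant will not stay that long. In addition, 7.1 says that when the early termination visit falls due within 4 weeks of a regular visit "it is appropriate to perform the procedures specified for the early termination visit at the appointed time in place of the regular scheduled visit". The two routes could therefore involve the same visits. Section 8.5.5 itself asks for the pregnancy outcome, so that information does not depend on which rule a site follows. All of this stands, and it is why the point is minor.

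Two further replies do not remove the conflict. First, 8.5.5 says must where 7.1 says should, so 8.5.5 might be taken to prevail. In that case 7.1 misdirects every site that consults the discontinuation section, and the text still needs correcting. Second, the sponsor-decision item in 7.2 is open-ended and might be stretched to cover pregnancy. That would supply a ground for withdrawal, but 7.1 would still say the opposite for the same event.

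It is also fair to say that the SAP Introduction declares the planned analyses no longer applicable and keeps them for reference. The analysis consequence is therefore one of design and will not affect a reported result.

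**Conclusion.** Wrong as written, and minor. Sections 8.5.5 and 7.1 give opposite instructions on study participation for the same event. Section 7.1 is the version that fits the safety follow-up period and the treatment policy strategy. No number of affected participants is claimed, because the documents give neither a pregnancy rate nor the share of women. The study was discontinued with four participants enrolled.

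A reader might infer more. The documents do not support the following:

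- **That the early termination ileocolonoscopy needs a pregnancy exemption.** Section 4.1 says "This visit will include a video ileocolonoscopy at the time of discontinuation, except those participants who have already had demonstrated endoscopic recurrence", and footnote f of the main Schedule of Activities says "Ileocolonoscopy does not need to be repeated if an ileocolonoscopy for a flare visit occurred within 12 weeks of the visit date". Neither mentions pregnancy. But the documents describe bleeding and perforation only as rare risks of the procedure in general and give no risk specific to pregnancy, so the argument would rest on outside knowledge. Footnote f also governs the Week 24, 48 and 152 procedures. A waiver added there would extend to the primary endpoint assessment.
- **That the same participant would count as a completer under one rule and as terminated under the other.** Section 4.4 lets anyone who stops early, for any reason, be counted as having completed the study after an early termination visit. Both routes stop study intervention and lead to that visit.
- **That a site following 7.1 would be logged with a major deviation.** SAP Appendix 4 has a category for meeting withdrawal criteria without being withdrawn, but the SAP does not define those criteria.
- **That the primary result is affected.** Nothing in the documents allows such an effect to be sized.

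**What to change.** Change one sentence in Protocol 8.5.5 so that a participant who becomes pregnant *must promptly discontinue further study intervention and be followed as described in Section 7.1*. Leave 7.1, 7.2, the Schedules of Activities, the intercurrent event handling and the SAP as they are.

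The cost is a single wording edit, with no new visits or procedures beyond those 7.1 already sets out. For this study the practical value is small. The main benefit is to avoid carrying the conflict into a later protocol that reuses the text.
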